**Figure 1. Study Design Schematic**

**Table 4: Periods, Study Day, and Visits**

PERIODS	SCREENING		TREATMENT			OBSERVATION		
STUDY DAYS	Day -21 to Day -1		Day 1	Day 7±2	Day 14±2	Day 28±4	Day 35±2	Day 56±4
VISITS	Screening Visit(s)	Day 1 Pre-Dose Visit	Day 1 Dosing Visit	Day 7 Visit	Day 14 Visit	Day 28 Visit	Day 35 Visit	Day 56 Visit
PURPOSE	
 
Screening Procedures
 
Baseline Assessments
 
Study drug application testing/ training
 
Randomization
 
PK sampling (PK Study Sub-Cohort)
 
		
 
Dosing Study Drug
 
Safety & Efficacy Assessments
 
PK sampling (PK Study Sub-Cohort)
 
Drug accountability
 
			
 
Safety & Efficacy Assessments
 
Day 35 PK sampling (PK Study Sub-Cohort)
 
		

## 7.2 Table of Study Assessments

Tables 5 and 6 are the Schedule of Assessments for all subjects enrolled in the trial. Table 6 is the Schedule of Assessments for subjects enrolled in the PK Study Sub-Cohort.

**Table 5: Schedule of Assessments for all Subjects**

Table 6, below, indicates the additional assessments to be performed on subjects enrolled in the PK sub-cohort.

Period Study Day Procedure\Visit	SCREENING PERIOD		TREATMENT PERIOD			OBSERVATION PERIOD			
	Day -21 to Day -1	Day 1		Day 7±2	Day 14±2	Day 28±4	Day 35±2	Day 56±4	Day 84±4
	Screening	Day 1 Pre-Dose	Day 1 Dosing	Day 7	Day 14	Day 28	Day 35	Day 56	Day 84
ICF procedures, signature, dating confirmed	√								
Enrollment criteria and/or safety data review	√	√							
Demographics and Medical History	√								
Adverse events reporting	√	√		√	√	√	√	√	√
Concomitant medications recorded	√	√		√	√	√	√	√	√
Vital signs	√	√		√ 	√	√	√	√	
Physical examination	√	√		√ 	√	√	√	√	
Height / Weight / BMI calculated	√								
12-Lead ECG	√	√		√ 	√	√			
Clinical laboratory testing	√	√		√ 	√	√			
Fitzpatrick skin type		√							
Treatment Field Selection	√	√							
AK lesions in the Treatment Field count and grade	√	√		√	√	√	√	√	√
Local Skin Reaction Score		√		√	√	√	√	√	√
Study drug measurement & application review	√	√ twice		√	√				
Pregnancy test (urine) at the site	√	√				√		√	
Subject randomization		√							
Application of the study drug each evening			√ Day 1 through Day 27						
Supervised study drug application at the site			√						
Trial instruction review / Closure procedure	√		√	√	√	√	√	√	√
Telephone contact by study staff		Once-weekly communication between site visits							
Photographs of Treatment Field (at selected sites only)		√						√	√
Study drug & tools given subject, as needed			√	√	√				
Study drug accountability/dosing compliance 		√		√	√	√			

 Only subjects enrolled in the Phase 1b Safety Cohort will undergo these assessments.

 Weigh study tube / record dates of any doses missed between Days 1 and 28

**Table 6: Table of Assessments for PK Study Sub-Cohort**

The following table indicates additional evaluations to those listed in Table 6 to be performed only in subjects enrolled in the PK Study Sub-Cohort.

Period	SCREENING PERIOD		TREATMENT PERIOD			OBSERVATION PERIOD			
	Day -21 to Day -1	Day 1		Day 7±2	Day 14±2	Day 28±4	Day 35±2	Day 56±4	Day 84±4
Study Day	Screening	Day 1 Pre-Dose	Day 1 Dosing	Day 7	Day 14	Day 28	Day 35	Day 56	Day 84
Additional Exclusion Criteria	✓								
24-hour Holter monitor attached						✓			
Toxicology screen	✓								
Blood sampling for PK 		✓		✓	✓	4 ✓	✓		

 One pre dose PK sample will be collected at the Day 1 pre-dose Visit, At the Day 7, Day 14 and Day 28 Visits, a sample will be collected when the subject arrives at the site (or approximately 12 hours after the last study drug application the previous evening). At the Day 28 Visit, three additional PK samples will be collected at 15, 18 and 21 hours (±30 mins) after the Day 27 evening dose. A final sample will be collected at the Day 35 Visit, at any time during that visit with the time noted.

### 7.3 Nested Phase 1b Safety Sub-Cohort

The first 15 (PK and non-PK) subjects enrolled in the trial will undergo on Day 7 the safety examinations planned for all other subjects plus a physical examination, clinical laboratory tests, and an ECG assessment. Once all 15 subjects in this Nested Phase 1b Safety Sub-Cohort have completed their Day 7 Visit, available blinded safety data (including AEs, LSR scores, clinical laboratory results, and ECG data) from Day 1 through Day 7 will be reviewed within 10 business days by a safety committee consisting of 2 Board-certified physicians not involved in the trial and the Study Medical Monitor (a Board-certified Allergist and Internist). During this blinded interim safety review, enrolled subjects will continue dosing the study drug and study enrollment will remain open.

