**Observation Period (Day 29 through 84):**

Subjects will visit their respective investigative site on **Days 35 and 56** for efficacy and safety assessments. On **Day 84** subjects will return to the sites for their final efficacy and safety assessments. Subjects with continuing AEs will be scheduled for follow-up evaluation, as appropriate.

**Nested Phase 1b Safety Sub-Cohort:** The first 15 (PK and non-PK) subjects enrolled in the trial will undergo on Day 7 the safety examinations planned for all other subjects plus physical examination, clinical laboratory and ECG assessments. Once all 15 subjects in this Nested Phase 1b Safety Sub-Cohort have completed their Day 7 Visit, safety data (including AEs, LSR scores, clinical laboratory results, and ECG data) from Day 1 through Day 7 will be reviewed in a blinded fashion by a safety committee. During this blinded interim safety review, enrolled subjects will continue dosing the study drug and study enrollment will remain open.

**PK Study Sub-Cohort:** Of the approximate 84 subjects to be enrolled in this trial, a maximum of 18 subjects at select sites will undergo blood sampling for PK analysis on Day 1 Pre-Dose as well as on Days 7, 14, 28, and 35. In addition, the PK Study Sub-Cohort will undergo 24-hour cardiac Holter monitoring on Day 28. Subjects included in this Sub-Cohort may also be included in the Nested Phase 1b Safety Sub-Cohort if they are in one of the first 15 subjects to be enrolled into the study.

**Number of Randomized Subjects (planned):** Approximately 84 (3x28) subjects will be randomized in order to complete the study with at least 75 (3x25) subjects anticipated to be available for efficacy analysis.

**Maximum Time Subjects May Remain in the Study:** Subjects may participate in this study for a maximum of approximately 117 days (21 Screening Period + 32 Treatment Period + 64 Observation Period)

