### **(iii) Pharmacokinetics**

In preclinical PK studies, VDA-1102 was rapidly metabolized, forming jasmonic acid as its inactive primary metabolite, regardless of the animal species or the route of administration. In all cases, the amount of JA in the blood equaled or exceeded the concentrations of VDA-1102 in the blood. In a 28-day dermal toxicity study in male and female minipigs, 5%, 10% or 20% of VDA-1102 ointment was applied once daily to 10% of the body surface area. Blood levels of VDA-1102 were essentially below the LLOQ on Day 1 and very low and highly variable on Day 28. Blood concentrations of the primary metabolite jasmonic acid on Day 1 were detected only in the 20% VDA-1102 ointment group. On Day 28, blood levels of jasmonic acid were detected at all dose levels and were higher than that on Day 1, likely related to slow transdermal absorption as it appeared that steady state levels were present on Day 28.

In the completed Phase 1a clinical trial (Section 5.5 above), there were no detectable concentrations of VDA-1102 or its primary metabolite, jasmonic acid following a single-dose of approximately 250 mg of 5%, 10%, or 20% VDA-1102 that was applied once to a 25 cm^2 area on the forehead of healthy older-adult volunteers.

In the current study, approximately 84 subjects will be dosed once each evening for 28 days with approximately 200 mg of study drug. Eighteen subjects will be enrolled into a PK Study Sub-Cohort and will undergo plasma sampling on Days 7, 14, 28, and 35 for PK assessment. Holter monitoring will be performed for 24 hours on Day 28 in all subjects enrolled in the PK Study Sub-Cohort so that relevant ECGs tracings corresponding to peak levels (if detected) of VDA-1102 and/or jasmonic acid may be extracted once the PK/exposure data are available.

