### ✓ **Day 7 Visit**

On Day 7 ( $\pm 2$ ) the following procedures will be performed:

- Adverse event(s) recorded
- Concomitant medications documented
- Study drug accountability and dosing compliance: study drug tubes will be weighed, the results recorded, and diaries reviewed and photocopied. Study drug and/or tools will be replenished, as needed.
- Vital signs: oral temperature, peripheral blood pressure, heart rate, and respiratory rate will be recorded.
- Local Skin Reaction Score in the Treatment Field
- AK Lesions in the Treatment Field: count (11.1.5) and grading (11.1.1)
- Study Drug Measurement and Application review (see Section 13.6.3)

- **The first 15 subjects randomized (Nested Phase 1b Safety Cohort) will undergo:**

- 12-lead ECG tracing will be recorded as per the ERT manual. An original (duplicate) copy of the ECG is required for trial documentation. This ECG will also be transmitted to the central ECG laboratory
- Clinical laboratory tests: fasting status will be recorded
- Physical examination

The following additional procedures will only be performed on the Day 7 Visit only in subjects enrolled in the subjects enrolled in the **PK Study Sub-Cohort**:

- ❖ PK blood sampling approximately 12 hours after the Day 6 dose

- Subject Instruction Packet will be reviewed including appointment for the next visit.
- Study drug and study tools will be given to the subject, as needed.

- ✓ ***Day 7 through Day 13***

- Subjects will dose at home each evening approximately 2 hours before bedtime and record the application in the dosing diary.
- Site personnel will communicate with the subjects once a week (Section 10.1.6) in order to review the Subject Instruction Packet and Dosing Diary as well as to remind each subject of their next site visit.

- ✓ ***Day 14 Visit***

On Day 14 ( $\pm 2$ ) the following procedures will be performed:

- Adverse event(s) will be recorded
- Concomitant medications documented
- Vital signs: peripheral blood pressure, respiratory and heart rates, and oral temperature will be recorded
- Physical examination
- Clinical laboratory tests: Fasting status should be recorded
- 12-lead ECG tracing will be recorded as per the ERT manual. An original (duplicate) copy of the ECG is required for trial documentation. This ECG will also be transmitted to the central ECG laboratory

- Local Skin Reaction Score in the Treatment Field
- AK Lesions in the Treatment Field: count (11.1.5) and grading (11.1.1)

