### 5.2.3 Nested Phase 1b Safety Sub-Cohort

The first 15 (PK and non-PK) subjects enrolled in the trial will undergo on Day 7 the safety examinations planned for all other subjects plus a physical examination, clinical laboratory tests, and an ECG assessment. Once all 15 subjects in this Nested Phase 1b Safety Sub-Cohort have completed their Day 7 Visit, available blinded safety data (including AEs, LSR scores, clinical laboratory results, and ECG data) from Day 1 through Day 7 will be reviewed within 10 business days by a safety committee consisting of 3 Board-certified physicians not involved in the trial and the Study Medical Monitor. During this blinded interim safety review, enrolled subjects will continue dosing the study drug and study enrollment will remain open.

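### The only scheduled committee safety review in these documents stops at Day 7 data, although all 15 subjects will be past their Day 14 visit by its deadline

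*Protocol*

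**What the plan says.** Protocol 7.3 defines a nested Phase 1b sub-cohort: "The first 15 (PK and non-PK) subjects enrolled in the trial will undergo on Day 7 the safety examinations planned for all other subjects". They also have an ECG, laboratory tests and a physical examination at that visit. The review is triggered by the last of them: "Once all 15 subjects in this Nested Phase 1b Safety Sub-Cohort have completed their Day 7 Visit". Available blinded safety data (adverse events, local skin reaction (LSR) scores, laboratory results, ECGs) "from Day 1 through Day 7 will be reviewed within 10 business days by a safety committee". Meanwhile, "During this blinded interim safety review, enrolled subjects will continue dosing the study drug and study enrollment will remain open".

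The same window appears in the synopsis ("from Day 1 through Day 7 will be reviewed in a blinded fashion by a safety committee"), in Protocol 5.6.1(ii) and in SAP 5.2.3 ("from Day 1 through Day 7 will be reviewed within 10 business days by a safety committee consisting of 3 Board-certified physicians"). The word for available data in 5.6.1(ii), 7.3 and the SAP does not widen the window, because the same sentence fixes it at Day 1 to Day 7.

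Later data need no new procedure. Protocol Table 5 and section 12.4.2 give every subject laboratory tests, an ECG, a physical examination, LSR scoring and adverse event recording at Days 14 and 28. The Day 14 list includes "Clinical laboratory tests: Fasting status should be recorded".

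No other scheduled aggregate safety review is described. The interim analysis at about 50% (Protocol 17.4) concerns efficacy. Protocol 7.5.1 and 16.2.1 require individual serious events, severe events and potentially serious findings to reach the Medical Monitor within 24 hours.

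**The concern.** The secondary objective is the safety of 28 days of dosing. The committee looks once, while dosing and enrolment continue, and its written scope is the first quarter of the treatment course. Because the trigger is the last subject's Day 7, the earlier subjects have moved well beyond that point by then. A committee that follows the text could report no concern while later findings in the same 15 subjects sit in the database outside its scope.

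The protocol gives some reason to look later. On the 28-day minipig study, 5.6.1(iii) says: "On Day 28, blood levels of jasmonic acid were detected at all dose levels and were higher than that on Day 1". It offers slow absorption through the skin as the likely, not the established, explanation. Table 1 puts the minipig no-adverse-effect level for local toxicity at the 5% ointment, with minimal local effects at 10%, which is also a strength used here. Completed human exposure (5.5) is a single application in 12 subjects on active drug.

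**Working it through.** The documents give no figure for how much data will exist at the review, so there is none to reproduce. The check is calendar arithmetic.

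**Inputs**
- 15 subjects; trigger at the 15th subject's Day 7; review within 10 business days, taken as 14 calendar days (Protocol 7.3).
- Visit windows: Day 7 ±2, Day 14 ±2, Day 28 ±4 (Table 5).
- Data entry within 5 business days, taken as 7 calendar days (Protocol 18.1).
- 84 subjects, 11-month duration, at most 117 days per subject (synopsis).
- Accrual rate: not stated, so assumed.

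**Step 1: no accrual assumption.** At the deadline the 15th subject is at Day 7 + 14 = Day 21. Every earlier subject is further on, so all 15 have passed nominal Day 14. At the extreme of the windows, a Day 7 visit held on Day 5 puts the deadline at Day 19, still after a Day 14 visit held on Day 16. With the entry lag, nominal visits are entered by Day 14 + 7 = Day 21, just in time. At the extreme windows they may not be (16 + 7 = 23, against 19).

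**Step 2: assumed accrual.** 11 × 30.44 = 334.8 days. Subtracting 84 to 117 days of follow-up leaves 250.8 to 217.8 days for 84 subjects. The first 15 then span 14 × 250.8/84 = 41.8 days down to 14 × 217.8/84 = 36.3 days. I use 35 to 42 days, an interval *i* of 35/14 = 2.5 to 42/14 = 3.0 days.

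**Step 3: counts.** Subject *k* is at Day 7 + (15 − *k*)*i* at the trigger and Day 21 + (15 − *k*)*i* at the deadline. The entry lag subtracts 7.
- Day 14 at the trigger needs (15 − *k*)*i* ≥ 7, so 15 − *k* ≥ 3 for either interval: 12 subjects.
- Day 28 at the trigger needs (15 − *k*)*i* ≥ 21: 6 subjects (*i* = 2.5) to 8 (*i* = 3.0).
- Day 28 at the deadline needs (15 − *k*)*i* ≥ 7: 12 subjects. With the lag the condition becomes ≥ 14: 9 to 10.

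| Days over which the first 15 enrol | Trigger: Day 14 / Day 28 | Trigger, after lag | Deadline: Day 14 / Day 28 | Deadline, after lag |
|---|---|---|---|---|
| 7 | 1 / 0 | 0 / 0 | 15 / 1 | 15 / 0 |
| 14 | 8 / 0 | 1 / 0 | 15 / 8 | 15 / 1 |
| 21 | 10 / 1 | 5 / 0 | 15 / 10 | 15 / 5 |
| 35 | 12 / 6 | 9 / 3 | 15 / 12 | 15 / 9 |
| 42 | 12 / 8 | 10 / 5 | 15 / 12 | 15 / 10 |

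Random (Poisson) accrual at 11.2 per month gives means of 11.4 (Day 14) and 6.3 (Day 28) at the trigger, and 15.0 and 11.4 at the deadline.

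**Step 4: exposure covered.** The Day 7 cut covers 15 × 7 = 105 subject-days. Counting treatment to Day 27, the 15 subjects have accrued about 395 of a possible 15 × 27 = 405 by the deadline, so the cut covers 105/395 ≈ 27%. After the entry lag about 364 to 370 are visible, and the share is 28% to 29%.

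**The case against.** **It is a deliberate early check.** The extra Day 7 tests exist only for these 15 subjects, and a fixed cut gives every subject the same window. No passage contradicts it. This stands, and it is why Day 7 should remain the complete core dataset. It gives no reason to exclude later data already collected.

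**Other oversight exists.** A reader might infer that this is the only safety oversight. It is not: besides 24-hour reporting, ECGs are read centrally, and the Medical Monitor who receives the reports sits on the committee. But that route works case by case and has filters. LSRs within the field and its 2 cm border are not adverse events unless they need prescription medication (15.1). Laboratory changes are not adverse events unless listed conditions apply (15.5). A gradual rise across subjects could pass beneath both. The protocol also defers adverse event details to a Safety Monitoring Plan that is not among these documents, so an aggregate review described there cannot be ruled out.

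**The toxicology is reassuring.** A reader might infer that the minipig data predict cumulative systemic harm. They do not. The metabolite is described as inactive, and parent drug at Day 28 was very low and variable. In 5.6.1(ii), 28 days at 5% or 10% gave no significant systemic findings and only mild, reversible skin findings. Table 1 puts the systemic no-adverse-effect level at 20%.

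**Reaching a visit is not having its data.** True. Entry takes up to 5 business days and queries up to 3 more, hence the lagged columns.

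**The review may already be over.** The SAP is Revision 2.0, dated May 2017, and refers to more than one protocol amendment. The documents do not say whether these 15 subjects had been reviewed by then.

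**Conclusion.** The point holds as a worthwhile, low-cost improvement to a design choice. The only scheduled aggregate committee safety review described is confined to Day 1 to 7 data on 15 subjects, while more of the same subjects' data will exist when it falls due.

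The Day 14 result (all 15 past the nominal visit by the deadline) needs no accrual assumption, only that the subjects remain in follow-up and that the review uses its full 10 business days. If the review is held at the trigger, the count depends on accrual. The Day 28 result (about 12 of 15, or 9 to 10 with data entered) rests on even accrual over the period implied by 11 months. It shrinks to one or none with entered data if the first 15 enrol within two weeks.

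A reader might also infer that the 28-day safety objective goes unmet. That is not supported: the final safety analysis covers the whole ITT population through follow-up (Protocol 17.2.2, SAP 5.6.7). What is lost is the chance for the committee to see a pattern earlier.

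**What to change.** In the protocol synopsis, Protocol 5.6.1(ii) and 7.3, and SAP 5.2.3, leave the Day 7 trigger, the committee and the blinding as they are. Keep the complete Day 1 to 7 dataset as the common core. Extend the scope to all blinded safety data (adverse events, LSR scores, laboratory results, ECGs) available on the 15 sub-cohort subjects at the data cut for the review, including any Day 14 and Day 28 visits, and state how that cut date is set. Widening it to every dosed subject is not needed to close this gap.

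The cost is a wording change in four places and a larger extract, with later visits incomplete for the last-enrolled subjects. No visit, test or reviewer is added. The same edit should reconcile the committee's size: two physicians plus the Medical Monitor in Protocol 7.3, three plus the Medical Monitor in SAP 5.2.3.

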### 7.4 PK Study Sub-Cohort

Of the approximate 84 subjects to be enrolled in this trial, a maximum of 18 subjects (who meet more stringent enrollment criteria than the other subjects enrolled) at select sites, will undergo blood sampling for PK analysis on Day 1 Pre-Dose as well as on Days 7, 14, 28, and 35 (Table 6). In addition, these subjects will undergo 24-hour cardiac Holter monitoring on Day 28 so that ECGs may be extracted based upon the other safety findings and the plasma PK data.

Subjects included in this sub-cohort may also be included in the Nested Phase 1b Safety Sub-Cohort if they are one of the first 15 subjects to be enrolled into the study.

## 7.5 Safety Reporting

### 7.5.1 Expedited Reporting to Sponsor and CRO

In addition to the reporting requirements for serious adverse events (SAEs) described in Section 16, all severe AEs must be reported to the Study Medical Monitor and the site's CRO contact within 24 hours.

All dose holidays and adjustments (described in Section 7.6 below) must be reported to the Study Safety Monitor (Sponsor) and the site's CRO contact within 24 hours. Such occurrences must be documented in the eCRF along with the reason for their occurrence.

In addition, if at any time during the course of the trial a potentially serious safety finding is noted by an Investigator, the Sponsor's Study Medical Monitor and the site's CRO contact must be notified within 24 hours.

## 7.6 Dose Holidays and Adjustments

Subject may be offered the following options at the Investigator's discretion:

- a) To temporarily stop the study drug for up to 7 days and to re-assess within that period;
- b) To temporarily stop the study drug for up to 7 days and instruct the subject to re-start the study drug application every other evening. The study drug may even be advanced to once-daily application as tolerated; or
- c) To stop the study drug for the duration of the trial but follow the subject otherwise as planned.

Bland moisturizers may be recommended at any time to any subject to manage LSRs. However, the moisturizer should be applied no sooner than 6 hours after dosing and the Treatment Field should be washed with mild soap before the next study drug application.

## 7.7 Study Endpoints

**Primary Efficacy Endpoint:** Change from baseline in the number of AK lesions within the Treatment Field of each subject on Day 56.

**Safety Endpoints:** Assessment of AEs, vital signs, physical examinations, clinical laboratory parameters, Local Skin Reaction (LSR) Scores, and electrocardiograms.

**Pharmacokinetic Endpoint:** Assessment of the systemic exposure of VDA-1102 and its primary metabolite jasmonic acid at selected time points during topical application of 5% or 10% VDA-1102 ointment for 28 days in adult subjects with AK.

**Exploratory Endpoints:** The percentage of subjects achieving complete clearance of AK lesions within the Treatment Field on Day 56.

Change from baseline in the number of AK lesions within the Treatment Field of each subject on Day 84.

